- Severe smoker (>10 cigarettes per day)

- Acute infections.
- Allergies to the material (if an allergy of any kind is suspected, adequate exams must be carried out in advance)
- Refusal of the patient to adhere to surgical follow-up and to the limit in activity level
- Fever and/or local inflammation
- HIV positive known
- History of uncontrolled diabetes (untreated or not stabilized by treatment)
- History of treatments for previous corticosteroids, long-term (more than 6 months) and interrupted for less than 3 months
- History of chemotherapy in progress or during the last three months
- History of cervico-facial radiotherapy
- History of bone disease with disorders of blood circulation which is defined as Albers-Schönberg disease or Paget's disease
- Known severe hyperparathyroidism
- History of severe immune deficiency

V.3. FEASIBILITY AND RECRUITMENT PROCEDURES

Coordinating Investigator

[name], PhD, Doctor of Dental Surgery (DDS) Associate professor Dental Faculty Nantes University Hospital, France.

Other Investigators

- [name], PhD, DDS, Associate professor Dental Faculty Nantes University Hospital, France.
- [name], PUPH, PhD, DDS, Dental Faculty Nantes University Hospital, France.
- [name], PUPH, PhD, DDS, Dental Faculty Nantes University Hospital, France.

Centers involved in the clinical investigation

Two centers will be involved in the clinical study. They already use Biomatlante RCM for GBR and GTR in oral/maxillofacial bone defects:

	Center n°1: Dental Care Center - Nantes University Hospital	Center n°2 Private Dental Practice – [name]	
Principal Investigator	[name]	[name]	
	[name]		
Investigators	[name]		
	[name]		

Each center will perform treatment in oral maxillofacial defects and will participate to patient recruitment during the whole study. The patients will be recruited during the consultations.

V.4. ACTIONS UPON PATIENT WITHDRAWAL

If a patient withdraws prematurely from the study, study personnel should make every effort to complete the full panel of assessments scheduled until the 12-week visit. The reason for patient withdrawal must be documented in the electronic case report form (eCRF).

Participation of a patient in this clinical study may be discontinued for any of the following reasons:

- The patient withdraws consent or requests discontinuation from the study for any reason;

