- Occurrence of any medical condition or circumstance that exposes the patient to substantial risk and/or does not allow the patient to adhere to the requirements of the protocol;
- Any SAE, clinically significant adverse event, which indicates to the Investigator that continued participation is not in the best interest of the patient;
- Pregnancy;
- Patient failure to comply with protocol requirements or study-related procedures; or
- Termination of the study by the Sponsor or the regulatory authority.

In the case of patients lost to follow-up, attempts to contact the patient must be made and documented in the patient's medical records.

Withdrawn patients will not be replaced.

VI. STUDY INTERVENTION

VI.1. **DEVICE DESCRIPTION**

This medical device is a Resorbable Collagen Membrane intended for use in Guided Tissue Regeneration or Guided Bone Regeneration procedures.

The Resorbable Collagen Membrane is crosslinked according to a controlled manufacturing process in accordance with current standards. Type I and III collagen fibres are extracted from the porcine epidermis and purified.

The Resorbable Collagen Membrane is hydrophilic and provides a barrier function for 12 weeks to prevent colonization of the surgical site by cells of connective and epithelial tissues.

The Resorbable Collagen Membrane allows the diffusion of biological fluids for a total resorption in 24 weeks.

The Resorbable Collagen membrane is easy to handle. Flexible, it adapts perfectly to all bone geometries.

The Resorbable Collagen Membrane is available in several dimensions: 15x25mm, 20x30mm and 30x40mm.

VI.2. INTENDED USE

The Resorbable Collagen Membrane is intended for use in Guided Tissue Regeneration or Guided Bone Regeneration procedures.

The claimed performance of the Resorbable Collagen Membrane is as follows: a barrier function that prevents the colonization of bone defect by connective and epithelial tissues.

VI.3. SURGICAL INTERVENTION

The Resorbable Collagen Membrane is indicated for the treatment of oral and maxillofacial bone defects and in periodontal diseases. This membrane is exclusively reserved for adults. It has not been tested on pregnant or breastfeeding women.

During this study, the investigators' practices will not be modified. For each type of surgery, the surgeon will perform all his acts in accordance with his current practice, without adding any additional procedure.

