The Resorbable Collagen Membrane should be handled in accordance with the manufacturer's recommendation using gloves and/or sterile instruments. This membrane can be cut to the appropriate shape and can be used directly or previously hydrated to facilitate its handling, especially when the surgeon intends to shape or fold the membrane at the implantation site.

The Resorbable Collagen Membrane can be sutured for better immobilization. The manufacturer recommends that the implant site be completely closed to avoid exposure of the Resorbable Collagen Membrane.

VI.4. CONTRAINDICATIONS

- Acute infections
- Known collagen allergies (if any type of allergy is suspected, adequate tests should be performed in advance)
- Fever and/or local inflammation

VI.5. AUTHORIZED OR FORBIDDEN TREATMENTS AND PROCEDURES

No prior or concomitant medication will be prohibited.

VII. STUDY ASSESSMENTS AND PROCEDURES

VII.1. MAIN EVALUATION CRITERION

This principal objective is to observe the performance of the RCM at 1, 2 and 12 weeks post surgery in terms of tissue regeneration. It will be assessed by the evaluation of mucose health on the implantation site at the different times of follow-up. The mucosa aspects that will be reported are the following: swelling, wound closure and colour.

- Swelling is defined by the presence of one or more swellings in the wound. The total absence of swelling at 12 weeks will be considered as the efficacy endpoint. This swelling is assessed subjectively by the investigator with the naked eye or by photography.
- Mucosal healing is characterized by wound closure. Complete wound closure will be considered as the efficacy criterion. This wound closure is assessed subjectively by the investigator with the naked eye or by photography.
- The colour at the implantation site can take on 3 aspects: pink identical to the surrounding mucosa Red. Pink colours and identical to the surrounding mucosa will be considered as the efficacy criteria. This colour is assessed subjectively by the investigator with the naked eye or by photography.

VII.2. SECONDARY EVALUATION CRITERIA

The secondary ojectives are to evaluate the safety of the RCM during the 12 weeks follow-up and evaluate the radiographic analysis of periodontal tissues.

The evaluation of the safety will be conducted by recording all the adverse events from screening through the 12-week visit (12 weeks \pm 1 week).

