- Allergy

Some side effects may be treated with medication or require reoperation.

VII.3.4. ADVERSE EVENTS REPORTING

Complete and accurate data on all AEs experienced for the duration of the reporting period, will be reported in the eCRF.

It is important that each AE report includes a description of the event, whether it is considered serious, its duration (onset and resolution dates), its severity, its relationship to the investigational product, any other potential causality factors, any treatment given or other action taken and its outcome.

As defined in Article R5212-17 of the French Public Health Code, all incident or risk of incident resulting from the use of a medical device brought to the investigator's attention will be the subject of a spontaneous report from the investigator to the local vigilance correspondent on whom he depends or, failing that, to the French National Agency for the Safety of Health Products (Agence Nationale de Sécurité et du Médicament = ANSM) in accordance with the usual procedures in force.

These declarations should be addressed at :

Direction de la surveillance – Plateforme de réception et d'orientation des signalements E-mail: [contact] [contact]

All AEs occurring from the time of informed consent until end of study participation must also be reported to the Sponsor.

All AEs that the Investigator considers related to the medical device occurring after the end of study participation must be reported to the Sponsor.

To report the AE, the AE form can be filled. When the form is completed, signed and dated, it must be sent to the Sponsor, specifically to the vigilance contact:

Vigilance contact :

[name] Quality Assurance Manager E-mail: [contact] [contact]

Immediately after receiving the follow-up information, the Investigator must update the AE form and submit any supporting documentation (e.g., patient discharge summary or autopsy reports) to the Sponsor.

For any research involving the human, where an unexpected serious adverse reaction or a new fact relevant to the research or product under investigation is likely to prejudice to the safety of the appropriate persons, the proponent and the Investigator shall take appropriate urgent safety measures.

VII.3.5. NEW FACTS REPORTING

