For the primary endpoint of effectiveness as measured by the performance of the RCM (binary endpoint) with a 90% target frequency (as hypothesized) and a confidence level of 95%, the following precisions can be achieved. The calculation was made using SAS[®].

Precision	Target frequency of performance	Number of patients to evaluate	Number of patients to recruit
8.3%	90%	50	56
6.8%	90%	75	83
5.9%	90%	100	111
5.3%	90%	125	139
5.0%	90%	150	165

Table 2 Sample size determination

With 50 patients, a precision around 8.3% can be achieved.

Accounting for a maximum of 10% dropouts or missing data, 56 patients should be recruited in the cohort.

VIII.2. ANALYSIS SETS

Four populations will be defined:

- Screened population will include all patients entering the study,
- Safety Set (SS) population will include all patients who received the RCM product,
- Full Analysis Set (FAS) efficacy population will include all patients who received the RCM product and in whom at least one efficacy information has been collected after the application of the RCM,
- Per-Protocol (PP) efficacy population will include all patients in FAS population without any major protocol deviation.

Remark: according to the ICH E9 recommendations, this subset of patients corresponds to a subset of the full "intention-to-treat" analysis set (including all randomized patients), being the full analysis set (FAS).

VIII.3. MISSING VALUES AND DROP-OUT

For the primary analysis (FAS analysis), a patient with missing data on the one of primary efficacy endpoint (swelling, wound closure or colour of the implantation site) will be considered as non efficacy of the product for this patient. Sensitivity analyses will be performed according to the following scenarios:

- No missing data will be imputed
- The missing data for the one of primary efficacy endpoint (swelling, wound closure or colour of the implantation site) will be considered as efficacy of the product.

VIII.4. STATISTICAL ANALYSIS

VIII.4.1. GENERAL CONSIDERATION

A Statistical Analysis Plan will be written by the biostatistician detailing the statistical analysis. The document will constitute the reference document as far as statistical analyses and methodologies are concerned. This document will be approved and signed by the Sponsor and the Principal Investigator before the first database lock.

The statistical analysis will be performed on SAS® version 9.4 or later (or equivalent statistical software).

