Quantitative variables will be described by the number of values entered, the number of missing data, the mean, the standard deviation, the 95% CIs for the means, the median, the 1st and 3rd quartiles, the minimum and maximum.

Qualitative variables will be described by the number of data filled in, the number of missing data, the frequency and the percentage of each modality. The 95% CIs of the percentages will be performed using exact confidence limits method.

All variable in the database will be described using descriptive statistics and all individual data will be presented in listings.

An interim analysis is planned in this study protocol in order to obtain the first results for December 2019. No sub-group analysis is planned.

VIII.4.2. ANALYSIS OF THE PRIMARY ENDPOINT

The primary endpoint analysis will be performed on FAS population. The primary endpoint will be analyzed on the PP population if the difference in the number of subjects between FAS and PP is more than 10%.

The primary efficacy endpoint is the mucosa aspects reported by swelling, wound closure and colour.

The composite primary endpoint will be summarized using descriptive statistics with binary outcome.

For patients who do not have swelling on the surgical site, with a complete wound closure on the surgical site and pink colour or identical colour to the surrounding mucosa on the surgical site, the investigational product will be considered as efficacious. If at least one of the primary endpoint performance is not satisfied, the investigational product will be considered ineffective for the patient.

Sensitivity analyses using different analyses sets and missing data handling as described above will be performed (see section "Missing values / dropouts"). The PP analysis will be considered as confirmatory analysis.

VIII.4.3. SAFETY ANALYSES

The safety analysis will be performed on SS population.

Safety endpoints will be AEs and SAEs all through the study.

AEs will be coded using MedDRA dictionary (latest version available). AEs will be classified according to period of occurrence: pre-treatment AEs and Treatment-Emergent AEs.

- Pre-treatment AEs are defined as adverse events occurring before the introduction of the investigational product.
- Treament-Emergent AEs are defined as an adverse who that emerges after introduction of the investigational product having been absent pre-treatment, or worsens relative to the pre-treatment state.

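### As the scoring rule is written, a patient re-operated for a side effect before week 12 who then looks healed counts as a success of the membrane, so the performance rate can be overstated

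*Combined protocol and SAP*

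**What the plan says.** The primary endpoint is a binary composite defined in VIII.4.2. The success rule opens "For patients who do not have swelling on the surgical site, with a complete wound closure on the surgical site" and adds a third sign, a pink colour or one matching the surrounding mucosa. The failure rule is the complement: "If at least one of the primary endpoint performance is not satisfied, the investigational product will be considered ineffective for the patient". Neither sentence sets any other condition, and neither names a visit.

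The visit has to be inferred. VII.1 lists readings at 1, 2 and 12 weeks but says of swelling: "The total absence of swelling at 12 weeks will be considered as the efficacy endpoint". The hypothesis in II.3 and the 90% target in VIII.1 are both set at 12 weeks.

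After listing the adverse events expected from the membrane, VII.3.3.3 adds: "Some side effects may be treated with medication or require reoperation". VI.1 says the membrane "provides a barrier function for 12 weeks to prevent colonization of the surgical site", which is the same period as the endpoint.

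On who is analysed, VIII.4.2 states: "The primary endpoint analysis will be performed on FAS population". Under VIII.3, a missing component "will be considered as non efficacy of the product for this patient". For patients who withdraw, V.4 asks that "study personnel should make every effort to complete the full panel of assessments scheduled until the 12-week visit".

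**The concern.** The protocol acknowledges an event that bears directly on how the membrane performed, yet the success rule does not look at it. A site that became infected, was re-operated and closed by week 12 meets all three signs. It is then credited to the product, although the healing followed a second procedure within the period for which the barrier function is claimed.

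The plan is also uneven. A patient with no week-12 reading is a failure in the primary analysis, while a patient who needed a second operation and then healed is a success. With one arm and no comparator, nothing offsets this. Compared with a rule that counts such patients as failures, the present rule can only give an equal or higher rate.

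**Working it through.** **Step 1. Reproduce the planning figure.** Inputs from VIII.1: target 90%, 95% confidence, 50 evaluable patients, 10% dropout.

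- Half-width: 1.96 × √(0.9 × 0.1 / 50) = 0.0832, or 8.3 points, as stated.
- Recruitment: 50 / 0.9 = 55.6, rounded up to 56, as stated.

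**Step 2. Follow a re-operated, healed and assessed patient through the plan.**

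- Full analysis set (VIII.2): the patient received the membrane and has efficacy data, so stays in.
- Missing-data rule and its two sensitivity scenarios (VIII.3): these act only on missing components, and none is missing.
- Follow-up (V.4): assessments are sought to week 12 even after withdrawal, so a healed reading can exist.
- Per-protocol set (VIII.2, X.5): exclusion depends on a major deviation graded at the data review meeting, and reoperation is not among the listed examples, which are not exhaustive. Exclusion would also remove the patient from the denominator rather than count a failure.
- Membrane performance, meaning barrier effect and exposure (IV.3, note d): recorded, but outside the composite.
- Action taken with the product and other action taken (VIII.4.3): summarised in the safety tables, with no link to the endpoint.

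None of these changes the patient's score.

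**Step 3. Size.** The documents give no reoperation rate, so the number k of such patients is an assumption. Start from 45 successes in 50. The interval is the exact (Clopper-Pearson) one, the method VIII.4.1 names. For x = 45 − k and n = 50, the lower limit is the 2.5% quantile of Beta(x, n − x + 1) and the upper limit is the 97.5% quantile of Beta(x + 1, n − x).

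| k recounted as failures | Rate | Exact 95% CI |
|---|---|---|
| 0 | 45/50 = 90.0% | 78.2 to 96.7 |
| 1 | 44/50 = 88.0% | 75.7 to 95.5 |
| 2 | 43/50 = 86.0% | 73.3 to 94.2 |
| 3 | 42/50 = 84.0% | 70.9 to 92.8 |
| 4 | 41/50 = 82.0% | 68.6 to 91.4 |
| 5 | 40/50 = 80.0% | 66.3 to 90.0 |

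Each patient is worth 1/50 = 2.0 points. If all 56 recruited patients were in the denominator, each would be worth 1/56 = 1.8 points.

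**Step 4. Would the per-protocol analysis reveal it?** With k = 3 and all three excluded, the rate is (45 − 3)/(50 − 3) = 42/47 = 89.4%. That is close to the 90% reported and well above the 84% obtained when they count as failures.

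**Step 5. How likely is k of at least 1?** This is again an assumption. If the true share of re-operated, healed and assessed patients were 1, 2, 5 or 10%, the expected number among 50 would be 0.5, 1, 2.5 or 5. The chance of at least one, 1 − (1 − r)^50, would be 39, 64, 92 or 99%.

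**The case against.** The strongest reply is that the rule answers the question the protocol asks. The hypothesis in II.3 concerns patients who undergo a procedure involving the membrane and their state at 12 weeks. The main objective in III.1 is performance as seen in swelling, closure and colour. Reading the mucosa at week 12 whatever happened in between is a legitimate estimand. This stands in part: the rule could be a deliberate choice. The plan does not say so, however, and it words the result as efficacy of the product, so the choice needs to be explicit.

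Second, a reader might infer that the reported rate is overstated. The documents do not support that. It follows only if such patients occur, heal and are assessed, and no rate is given. Shifts of 2 to 6 points also lie inside the planned 8.3. That comparison is limited, because 8.3 describes sampling error and this shift would come on top of it. It is true that the study is descriptive and sets no pass mark.

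Third, a reader might infer that the plan anticipates removal of the membrane. It does not. Removal or replacement is never named as an event, and II.2 counts the absence of a second operation for removal as an advantage of resorbable membranes. VII.3.3.3 speaks of reoperation, and only as a possibility.

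Fourth, VIII.4.2 names no visit. If the signs also had to be met at weeks 1 and 2, some of these patients would already be failures. Week 12 is the better reading, but it remains an inference.

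Fifth, these events are not hidden: the safety tables and individual listings would show them. That discloses them but leaves the primary rate as it is. The separate SAP announced in VIII.4.1 could supply the rule, but the protocol does not say that it will.

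Finally, counting every reoperation as a failure would charge planned or unrelated procedures to the membrane. That objection is sound, and the fix is limited accordingly.

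**Conclusion.** The point holds as a conditional one. Under the stated rule, a patient re-operated at the treated site because of a side effect before week 12, then healed and assessed, is scored as a product success, and no other provision prevents it. If such patients occur, the rate is 2 points too high for each of them at n = 50, relative to a rule that counts them as failures. With three, 90% (78.2 to 96.7) becomes 84% (70.9 to 92.8); with none, nothing changes.

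This rests on three assumptions: the number of such patients, which the documents do not give; week 12 as the scoring visit; and performance meaning healing without an unplanned second procedure. It does not show that the rate will be wrong, nor that membrane removal is an expected event. It is a gap in the endpoint definition that should be closed before results are seen, since the study is open-label, the signs are judged subjectively and an interim analysis is planned.

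**What to change.** Before the first database lock, including any lock for the interim analysis, add to VIII.4.2 or the SAP:

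- An unplanned re-intervention at the treated site before the 12-week assessment, made for a device- or healing-related adverse event, counts as non-efficacy in the primary composite. Loss or removal of the membrane is included, should it happen. This is a scoring rule for the analysis only and has no bearing on patient care.
- Planned procedures, and procedures unrelated to the device or to healing, do not count.
- The visit at which the composite is scored is named.
- The number of patients reclassified is reported, and the result under the mucosa-only rule is shown alongside.

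The derivation uses the adverse-event items on treatment or other action taken and on relationship to the product, which VII.3.4 already requires. Whether the eCRF identifies a re-intervention as being at the treated site is not stated, so this has to be confirmed and, if necessary, an item added.

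The cost is a few lines of SAP text, one derivation and one extra table. The downside is that the reported rate may be slightly lower. If the sponsor prefers to keep the mucosa-only rule as primary, it should say so and give the reason, and present the failure-scored result as a sensitivity analysis.
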